 - a. Lansky score \geq 40 ([Appendix 1](#)) or
 - b. Karnofsky score $>$ 50 ([Appendix 2](#)) or
 - c. Eastern Cooperative Oncology Group (ECOG) score \leq 2 ([Appendix 3](#))
8. Have adequate bone marrow reserves and liver and kidney function, as assessed by the following laboratory requirements:
 - a. Hemoglobin \geq 8 g/L
 - b. Absolute lymphocyte count \geq 500/mm³
 - c. Absolute neutrophil count \geq 1000/mm³
 - d. Platelets \geq 100,000/mm³ (untransfused [$>$ 5 days] without growth factors)
 - e. Serum creatinine \leq 1.5 x upper limit of normal (ULN) for age
 - f. Aspartate transaminase (AST) and alanine transaminase (ALT) \leq 2.5 x ULN for age
 - g. Total bilirubin $<$ 1.5 x ULN for age
 - h. International normalized ratio (INR) and activated thromboplastin time within normal institutional limits
9. Male and female subjects of childbearing potential must agree to use a highly reliable method of birth control (expected failure rate $<$ 1% per year) from the Screening visit through 28 days after the last dose of study drug. Women of childbearing potential must have a negative pregnancy test at screening.

Exclusion Criteria:

1. Radiotherapy treatment prior to the first veledimex dose:
 - a. Focal radiation \leq 4 weeks
 - b. Whole-brain radiation \leq 6 weeks
 - c. Cranio-spinal radiation \leq 12 weeks
- Note:** Subjects in Arm 2 (*i.e.*, with DIPG) must be \geq 2 weeks and \leq 10 weeks post standard focal radiotherapy (dose of 5400 to 5960 cGy and maximum dexamethasone of 1 mg/m²/day) per Inclusion Criterion 3 above.
2. Subjects with clinically significant increased intracranial pressure (*e.g.*, impending herniation or requirement for immediate palliative treatment) or uncontrolled seizures
3. Subjects whose body surface area (BSA) would expose them to $<$ 75% or $>$ 125% of the target dose per the provided dosing table
4. Known immunosuppressive disease, autoimmune condition, and/or chronic viral infection (*e.g.*, human immunodeficiency virus [HIV], hepatitis)
5. Use of systemic antibacterial, antifungal, or antiviral medications for the treatment of acute clinically significant infection within 2 weeks of first veledimex dose. Concomitant therapy for chronic infections is not allowed. Subjects must be afebrile prior to Ad-RTS-hIL-12 injection; only prophylactic antibiotic use is allowed perioperatively.

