Based on the planned Phase III dose (20 mg [approximately 10.6 mg/m²]) in the adult population, this study will explore the following BSA-adjusted veledimex doses given after Ad-RTS-hIL-12 [REDACTED] administration. The starting dose in Cohort 1 will be 10 mg, which is approximately 5.3 mg/m². The actual administered dose will depend on the subject's BSA and available capsule sizes. Because veledimex is an oral agent and is supplied in fixed capsule sizes (5 mg and 20 mg), the actual administered dose is based on a subject's BSA and is bound by the rounding constraints set by 5 mg. The Sponsor developed a BSA-adjusted dosing algorithm designed to enable dosing within 25% of the target mg/m² dose.

If a subject's BSA would expose the subject to < 75% or > 125% of the target assigned dose, the actual administered dose will be modified to ensure that the target mg/m² dose is achieved. Minimum BSA restrictions for enrollment must be met in order for a subject to be appropriately dosed.

Potential subjects whose BSAs do not have a correlated administered dose may be enrolled at the discretion of the Investigator and the Medical Monitor, but will not be considered in the assessment of the recommended Phase II pediatric dose. Dosing of these subjects can only commence once the cohort has been reviewed by the SRC and determined that the dosing at the specified level (10 mg or 20 mg) is appropriate for escalation or as the recommended Phase II pediatric dose. These subjects will be analyzed separately.

The dosing table illustrates this algorithm and captures the BSA-adjusted actual administered dose that subjects would receive at assigned dose levels based on a minimum capsule size of 5 mg.

Cohort	Target Dose (mg/m ²)	Min BSA (m ²)	Min BSA Target Dose (mg/m ²)	Percentage of Expected Dose (%)	Max BSA (m ²)	Max BSA Target Dose (mg/m ²)	Percentage of Expected Dose (%)	Actual Dose ^a (mg)
10 mg	5.3	0.5	10	189%	0.75	6.7	126%	5 mg ^b
10 mg	5.3	0.76	6.6	124%	1.26	4.0	75%	5 mg
10 mg	5.3	1.27	3.9	74%	1.5	3.3	63%	5 mg
10 mg	5.3	1.27	7.9	149%	1.5	6.7	126%	10 mg ^b
10 mg	5.3	1.51	6.6	125%	2.53	4.0	75%	10 mg
Cohort	Target Dose (mg)	Min BSA (m ²)	Min BSA Target Dose (mg)	Percentage of Expected Dose (%)	Max BSA (m ²)	Max BSA Target Dose (mg)	Percentage of Expected Dose (%)	Actual Dose ^a (mg)
20 mg	10.6	0.5	10	94%	0.63	7.9	75%	5 mg
20 mg	10.6	0.64	7.8	74%	0.75	6.7	63%	5 mg
20 mg	10.6	0.64	15.6	147%	0.75	13.3	126%	10 mg ^b
20 mg	10.6	0.76	13.2	124%	1.25	8.0	75%	10 mg

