The starting dose in Cohort 1 will be 10 mg, which is approximately 5.3 mg/m^2 . The actual administered dose will depend on the subject's BSA and available capsule sizes ([Table 4b](#)). Because veledimex is an PO agent and is supplied in a fixed capsule size (5 mg and 20 mg), the actual administered dose is based on a subject's BSA and is bound by the rounding constraints set by 5 mg. The Sponsor developed a BSA-adjusted dosing algorithm designed to enable dosing within 25% of the target dose in mg/m^2 .

If a subject's BSA would expose the subject to $< 75\%$ or $> 125\%$ of the target assigned dose, the actual administered dose will be modified to ensure that the target dose in mg/m^2 is achieved. Minimum BSA restrictions for enrollment must be met in order for a subject to be appropriately dosed. Potential subjects whose BSAs do not have a correlated administered dose may be enrolled at the discretion of the Investigator and the Medical Monitor but will not be considered in the assessment of the recommended Phase II pediatric dose. Dosing of these subjects can only commence once the cohort has been reviewed by the SRC and determined that the dosing at the specified level (10 mg or 20 mg) is appropriate for escalation or as the recommended Phase II pediatric dose. These subjects will be analyzed separately.

The dosing table ([Table 4b](#)) illustrates this algorithm and captures the BSA adjusted-actual administered dose that subjects would receive at assigned dose levels based on a minimum capsule size of 5 mg.

Table 4b: Veledimex Dosing Table

Cohort	Target Dose (mg)	Min BSA (m ²)	Min BSA Target Dose (mg)	Percentage of Expected Dose (%)	Max BSA (m ²)	Max BSA Target Dose (mg)	Percentage of Expected Dose (%)	Actual Dose ^a (mg)
10 mg	5.3	0.5	10	189	0.75	6.7	126	5 ^b
10 mg	5.3	0.76	6.6	124	1.26	4.0	75	5
10 mg	5.3	1.27	3.9	74	1.5	3.3	63	5
10 mg	5.3	1.27	7.9	149%	1.5	6.7	126%	10 mg ^b
10 mg	5.3	1.51	6.6	125%	2.53	4.0	75%	10 mg
Cohort	Target Dose (mg)	Min BSA (m ²)	Min BSA Target Dose (mg)	Percentage of Expected Dose (%)	Max BSA (m ²)	Max BSA Target Dose (mg)	Percentage of Expected Dose (%)	Actual Dose ^a (mg)
20 mg	10.6	0.5	10	94%	0.63	7.9	75%	5 mg
20 mg	10.6	0.64	7.8	74%	0.75	6.7	63%	5 mg
20 mg	10.6	0.64	15.6	147%	0.75	13.3	126%	10 mg ^b
20 mg	10.6	0.76	13.2	124%	1.25	8.0	75%	10 mg
20 mg	10.6	1.26	11.9	112%	1.87	8.0	75%	15 mg
20 mg	10.6	1.88	10.6	100%	2.53	7.9	75%	20 mg

^a The actual dose is \pm 25% of the target dose.

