^b Subjects in this BSA range may be dosed at the discretion of the Investigator and the Medical Monitor

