7.5. Recommended Phase II Pediatric Veledimex Dose and Corticosteroid Exposure

The recommended Phase II pediatric veledimex dose will be determined using the Evaluable Safety Population (ESP). The recommended pediatric Phase II dose is defined as the dose level below the dose in which $\geq 33\%$ of subjects in the same cohort experience DLTs. If 2 DLTs occur in the same cohort, dose escalation will stop in the cohort experiencing the DLTs. A decision to enroll additional subjects in an expansion cohort will be made by the SRC.

The recommended pediatric Phase II dose in this study will be determined in the context of variable corticosteroid exposure and will be reported as such. Investigational treatment requires that steroid use be allowed to manage brain tumor related symptoms or edema, especially after tumor resection. It is expected that the use and dose of corticosteroids will vary among trial sites and among subjects, and therefore, the extent and dose of steroids is not specified in this protocol. The treating physician should consider the minimum starting steroid dose for study subjects, if determined that it is safe and appropriate for that individual subject. For study subjects who require a higher starting steroid dose, efforts should be made to taper steroids to the lowest amount that controls the subjects' symptoms, as determined to be safe and appropriate by the treating physician.

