8.2. Exclusion Criteria

1. Radiotherapy treatment prior to the first veledimex dose:
 - a. Focal radiation ≤ 4 weeks
 - b. Whole-brain radiation ≤ 6 weeks
 - c. Cranio-spinal radiation ≤ 12 weeks
- Note:** Subjects in Arm 2 (*i.e.*, with DIPG) must be ≥ 2 weeks and ≤ 10 weeks post standard focal radiotherapy (dose of 5400 to 5960 cGy and maximum dexamethasone of 1 mg/m²/day) per Inclusion Criterion 3 above.
2. Subjects with clinically significant increased intracranial pressure (*e.g.*, impending herniation or requirement for immediate palliative treatment) or uncontrolled seizures
3. Subjects whose body surface area (BSA) would expose them to $< 75\%$ or $> 125\%$ of the target dose per the provided dosing table
4. Known immunosuppressive disease, autoimmune condition, and/or chronic viral infection (*e.g.*, human immunodeficiency virus [HIV], hepatitis)
5. Use of systemic antibacterial, antifungal, or antiviral medications for the treatment of acute clinically significant infection within 2 weeks of first veledimex dose. Concomitant therapy for chronic infections is not allowed. Subjects must be afebrile prior to Ad-RTS-hIL-12 injection; only prophylactic antibiotic use is allowed perioperatively.
6. Use of enzyme-inducing antiepileptic drugs (EIAEDs) within 7 days prior to the first dose of study drug. See [Appendix 4](#) for prohibited and permitted antiepileptic drugs.
7. Other concurrent clinically active malignant disease, requiring treatment
8. Nursing or pregnant females
9. Prior exposure to veledimex

10. Use of medications that induce, inhibit, or are substrates of CYP450 3A4 within 7 days prior to veledimex dosing without consultation with the Medical Monitor
11. Use of heparin or acetylsalicylic acid (ASA) without consultation with the Medical Monitor
 - a. The use of systemic heparinization, or any ASA containing medications, is prohibited during active dosing with veledimex. Prophylactic s.c. heparin, per institutional protocol, or heparin used for maintaining patency of an access port of PICC line is permitted.
12. Presence of any contraindication for a neurosurgical procedure
13. Unstable or clinically significant concurrent medical condition that would, in the opinion of the Investigator in conjunction with the Medical Monitor, jeopardize the safety of a subject and/or their compliance with the protocol

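### Exclusion criterion 3 and Table 4b footnote b contradict each other, and release is tied to the dose label: if 20 mg is rejected and 10 mg recommended, a 0.50–0.63 m² child may still get 5 mg (10.0–7.94 mg/m²)

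*Protocol*

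**What the plan says.** Exclusion criterion 3 (protocol 8.2 and synopsis) removes "Subjects whose body surface area (BSA) would expose them to" less than 75% or more than 125% "of the target dose per the provided dosing table". It states no exception.

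Protocol 7.1 and the synopsis then let children outside the window enrol by agreement between the Investigator and the Medical Monitor. Footnote b to Table 4b repeats this for three rows: "Subjects in this BSA range may be dosed at the discretion of the Investigator and the Medical Monitor". On timing, the synopsis says "Dosing of these subjects can only commence once the cohort has been reviewed by the SRC", and the SRC must have found that "the dosing at the specified level (10 mg or 20 mg) is appropriate for escalation or as the recommended Phase II pediatric dose". These children "will not be considered in the assessment of the recommended Phase II pediatric dose" and are analysed separately.

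On dose selection, 7.5 says: "The recommended pediatric Phase II dose is defined as the dose level below the dose in which" at least 33% of a cohort have DLTs. Protocol 7.3, Table 5 and 16.2 also allow de-escalation in 5 mg steps, with 15 mg named as the step after 20 mg.

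On populations, the protocol (synopsis, 14 and 16.1) requires members of the ESP to be BSA-conformant. SAP 5.3 defines the ESP without that condition and uses it for DLT evaluation and dose recommendation.

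**The concern.** A site reading section 8.2 must refuse the child; a site reading Table 4b may dose the same child. That conflict needs no particular trial outcome to matter.

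The second issue depends on an outcome. Clearance is given to a label (10 mg or 20 mg), but footnote-b doses under that label lie outside the mg/m² window on which the clearance rests. Table 4b prints 5 mg at 0.50–0.63 m² twice: as a footnote-b dose of the 10 mg level, and as an ordinary conformant dose of the 20 mg level. If 20 mg is rejected and 10 mg recommended, the row under the rejected label goes, but the identical dose under the surviving label stays available. At stake are which very small children are dosed after a toxicity finding, and whether their DLTs enter later dose decisions.

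**Working it through.** **Inputs.** Doses, BSA limits and targets (5.3 and 10.6 mg/m²) from Table 4b; smallest capsule 5 mg from protocol 7.1; the 75–125% window from 7.1 and criterion 3. Exposure = dose ÷ BSA; percentage = exposure ÷ target.

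**1. Reproducing Table 4b.**
- 10 mg level, 5 mg: 5/0.50 = 10.0 mg/m², and 10.0/5.3 = 188.7% (printed 189). 5/0.75 = 6.67, and 6.67/5.3 = 125.8% (printed 126).
- 20 mg level, 5 mg: 10.0/10.6 = 94.3% (printed 94). 5/0.63 = 7.94, and 7.94/10.6 = 74.9% (printed 75, with no footnote b, so treated as conformant).

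**2. Eligibility conflict.** The three footnote-b rows run 189–126%, 149–126% and 147–126% of target. Every row that the footnote opens is one that criterion 3 closes.

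**3. Size of the excess.**
- Highest conformant exposure at the 10 mg level: 10/1.51 = 6.62 mg/m² (the other conformant row peaks at 5/0.76 = 6.58).
- 5 mg at 0.50–0.63 m²: 10.0/6.62 = 1.51 and 7.94/6.62 = 1.20, so 51% to 20% above.
- Conformant range at the 20 mg level: 20/2.53 = 7.91 up to 10/0.76 = 13.16. The child's 7.94–10.0 lies in its lower part.
- The other 10 mg-label footnote-b doses are 5 mg at 0.64–0.75 m² (7.81–6.67) and 10 mg at 1.27–1.50 m² (7.87–6.67). Both stay below 7.91, so only the 0.50–0.63 m² band overlaps the 20 mg level.

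**4. Can the dose be lowered?** Protocol 7.1 says that the dose is adjusted to reach the target. The 125% limit is 1.25 × 5.3 = 6.625 mg/m², and 5/6.625 = 0.755 m². Below that BSA the smallest capsule already exceeds the limit.

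**5. Is the scenario reachable?** If at least 33% of the 20 mg cohort have DLTs, 7.5 points to the level below. If the SRC names 10 mg, the release condition is met, and no sentence closes the 5 mg row. If the SRC clears 15 mg instead, the answer depends on a target that Table 4b does not give. Assuming proportional scaling, 15/20 × 10.6 = 7.95 mg/m², with a window of 5.96–9.94; 5 mg then fits from 5/9.94 = 0.503 m², almost the whole band. For a range: the 0.63 m² end fits under the upper limit if the target is at least 7.94/1.25 = 6.35, and the 0.50 m² end if it is at least 10.0/1.25 = 8.0 mg/m².

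**6. Whose DLTs count?** Under the protocol the child is outside the ESP and outside the recommended-dose assessment. Under SAP 5.3 no BSA term keeps the child out. The SAP's major-deviation condition concerns interpretability of efficacy endpoints, and SAP 8 says no subject leaves a population because of a deviation. Because these children start only after cohort review, the difference bears on later assessments: the DLT tables in SAP 11 and any later SRC review.

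**The case against.** A reader might infer that the label alone releases these children and that exposure is unlimited. The documents do not support that. The Investigator and Medical Monitor must agree, the SRC must have reviewed the cohort, and Table 1 footnote n requires both to deem the subject eligible before registration. The Medical Monitor sits on the SRC and is contacted before each daily dose. Table 4b starts at 0.50 m², so the 10 mg label cannot exceed 10.0 mg/m², below the adult reference of about 10.6 ("Based on the planned Phase III dose"). What remains is that none of this is a written mg/m² limit, and an adult dose does not establish safety in children.

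A reader might also infer that 10 mg follows automatically once 20 mg fails, or that the child receives an exposure shown to be unsafe. Neither holds. A 15 mg level may come first, and continuing at 10 mg takes a deliberate SRC decision. DLTs across 7.9–13.2 mg/m² would not show that 7.94 is unacceptable. When 10 mg is merely cleared for escalation, the exposure point is weaker still, since the same child could enter Cohort 4 as conformant at the same 5 mg.

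It can be said that criterion 3 cites the table and the footnote is the table's own exception. That is probably the intent, but the criterion does not say so.

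Leaving these DLTs out of the dose assessment is defensible: an event at 150–189% of target says little about the 10 mg level, and the child stays in the OSP. That argues for aligning the SAP with the protocol. The 7.10 pause helps, but does not list two DLT types from 7.4: Grade 3 or higher non-haematologic events lasting at least 3 days, and Grade 3 or higher thrombocytopenia.

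**Conclusion.** The concern holds in a narrow form. The eligibility contradiction and the ESP discrepancy between protocol and SAP are plain from the texts. The exposure gap is conditional: 20 mg stopped for DLTs, 10 mg named as the recommended dose, no intermediate level cleared that covers the exposure, and a discretionary decision to dose. Then 5 mg at 0.50–0.63 m² gives 20–51% more than any conformant 10 mg-level subject receives and equals a conformant row of the rejected level.

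The number of such children is unknown and probably small: they must be very small, swallow capsules whole and be individually approved. A reader might go further and want a general cap at 125% of the highest cleared level. The documents do not support that: it would rest on an unstated 15 mg target and, with only 10 mg cleared, would shut out children at 0.75 or 1.50 m² for 6.67 against 6.625 mg/m². The wording should be changed; confidence is medium, because the rationale for this provision is not visible.

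**What to change.** 1. In 7.1 and the synopsis, state that if the 20 mg level is stopped or de-escalated for DLTs, the 10 mg-label dose of 5 mg at 0.50–0.63 m² is closed, unless the SRC has cleared an intermediate level whose stated mg/m² range covers that exposure. Any 15 mg level would then need its own target and BSA rows.
2. Write the footnote-b exception, with this limit, into exclusion criterion 3 in 8.2 and the synopsis, or remove footnote b.
3. Add the BSA-conformant condition to the ESP definition in SAP 5.3. In the SAP 13.2.2 exposure listing, which already groups subjects as below 75%, 75–125% and above 125%, show each discretionary child's actual mg/m² and any DLT.

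The cost is wording in two documents and a small addition to an existing listing, with no extra patients or procedures. A few very small children would lose discretionary access after 20 mg is rejected; removing footnote b outright would also end discretion for its other rows. The Amendment 1 summary places this dosing text among changes requested by the regulator, so the regulator's agreement may be needed.

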7.2. Study Oversight for Safety Evaluation

The first level of safety oversight will occur through the site Investigator in conjunction with the Medical Monitor. The site Investigator will communicate with the Medical Monitor during the active dosing period for all subjects on a daily basis regarding clinical status and laboratory values, prior to the patient receiving their daily dose of veledimex, and additionally as clinically indicated.

A formal Safety Review Committee (SRC), comprised of the study Investigators, the Medical Monitor, and other appropriate Sponsor representatives, will provide the overall safety oversight. Additional external medical and scientific experts may also be invited to participate in the reviews, as needed. A separate charter will outline the SRC activities. Briefly, the SRC will evaluate subject safety within each cohort. If no significant safety events occur with the first subject of each cohort, the second and third subjects will be enrolled and treated. If a significant safety event occurs with the first subject, the SRC will convene to evaluate the safety event(s) and to make a recommendation and decision on the enrollment of the second and third subjects in the same cohort.

Upon completion of each cohort, the SRC will meet to review the data collected to determine next steps as described in Section 7.3. Enrollment in Cohort 4, with the 20 mg assigned

veledimex dose will not commence until the SRC has determined that dosing at the lower level, Cohort 3, did not result in DLTs that would preclude dose escalation.

In addition to recommending the opening of Arm 2 Cohort 3, or dose escalation to Cohort 4, the SRC may also determine if the study should proceed with the Phase II portion (an expansion of an Arm 2 cohort). In the event that the SRC determines that escalation and/or expansion is not warranted, a decision will be made about stopping the investigation. At the discretion of the SRC, the investigation may be continued at a lower dose.

Dose escalation, cohort expansion, and de-escalation rules will be followed as defined in Section 7.3 and study stopping rules will be followed as defined in Section 7.10.

7.3. Dose Escalation, Cohort Expansion, and De-Escalation Decision Rules

Expansion cohort(s) are prospectively planned in this study, in Arm 2, at the discretion of the SRC.

Each subject in each dose escalation cohort (3+3 standard design) will be monitored for 28 days before subsequent subjects are enrolled. The SRC will convene after the third and/or final subject in each cohort completes the 28-day DLT evaluation period and will make a recommendation regarding expanding the current cohort by up to 30 additional subjects (phase II component), opening of the next cohort/dose escalating, dose de-escalating, or discontinuing the investigation.

If the SRC recommends expanding the current cohort, a 28-day review period may not be required between each patient. Based on the safety profile of the current cohort, the SRC will make a determination related to the waiting period.

The SRC will determine if/when the MTD is met and may recommend cohort expansion at that dose.

Study stopping rules will be followed as defined in [Section 7.10](#).

Dose Escalation/Cohort Expansion

Each subject in each dose escalation cohort (3+3 standard design) will be monitored for 28 days before subsequent subjects are enrolled. The SRC will convene after the final subject in Cohort 1 completes the 28-day DLT evaluation period. The SRC will make a recommendation regarding:

- Opening enrollment of Cohort 3
- Discontinuing the investigation

If the SRC recommends opening enrollment in Cohort 3, each subject will be monitored for 28 days before subsequent subjects are enrolled in the same cohort. The SRC will convene once the third and/or final subjects (*i.e.*.. subject 3 of 3 or 6 of 6) in Cohort 3 complete the 28-day DLT evaluation period. The SRC will make a recommendation regarding:

- Expansion of Cohort 3 (Phase II portion)
- Opening enrollment of Cohort 4
- Discontinuing the investigation

If the SRC recommends enrollment of Cohort 4, each subject will be monitored for 28 days before subsequent subjects are enrolled in the same cohort. The SRC will convene once the third and/or final subject (*i.e.*, subject 3 of 3 or 6 of 6) in Cohort 4 complete the 28-day DLT evaluation period. The SRC will make a recommendation regarding:

- Expansion of Cohort 4 (Phase II portion)
- Discontinuing the investigation

In addition to recommending dose escalation, cohort expansion, or discontinuation of treatment, as noted above, the SRC may recommend dose de-escalation at any point based on safety review.

Dose De-Escalation

If it is determined that dose escalation or cohort expansion should not proceed, dose de-escalation may be undertaken and the SRC will consider de-escalating the veledimex dose as follows:

- De-escalation by increments of 5 mg from the cohort in which 2 or more DLTs were observed (*e.g.*, 15 mg, de-escalated from 20 mg)
- If there are 2 or more DLTs in the dose de-escalation cohort, the SRC will consider stopping enrollment at that dose and de-escalating the veledimex dose by an additional increment of 5 mg (*e.g.*, 5 mg down from 10 mg) or declaring a previously studied dose level the recommended Phase II pediatric dose

If no DLTs occur among the three subjects in Cohort 1, dosing may proceed to the next cohort, Cohort 3, after the SRC provides their recommendation to proceed (Table 5). In any cohort, if one DLT occurs among the three subjects, three additional subjects will be enrolled. If one or more of the three additional subjects experience a DLT, dosing will stop. The SRC will then convene to evaluate safety, determine if the recommended Phase II dose has been reached per **Section 7.5**, and will decide whether to stop treatment or de-escalate veledimex dosing. The SRC may also seek an *ad hoc* safety evaluation and recommendation by external experts as needed.

Table 5: Dose Escalation and De-Escalation Decision Rules

Subjects with DLTs (Any Dose Level)	Decision Rule	Subject Count
None of the first 3 subjects OR ≤ 1 subject (in the case of a 6-patient cohort) experiences a DLT	Expand current dose level cohort or enroll the next higher dose level cohort (after SRC recommendation).	3 or 6
1 of the first 3 subjects experiences a DLT	Enroll at least 3 more subjects in this dose level cohort. If none of the 3 additional subjects experiences a DLT, expand current dose level cohort or proceed to the next planned dose level cohort (after SRC recommendation).	6

Table 5: Dose Escalation and De-Escalation Decision Rules (Continued)

Subjects with DLTs (Any Dose Level)	Decision Rule	Subject Count
2 or more subjects in a cohort experience a DLT	
If 2 subjects experience a DLT, then STOP dose escalation in the cohort experiencing the DLTs and do the following:
 
 The SRC will conduct a safety review to evaluate safety and determine whether the cohort experiencing the 2 DLTs has met the definition of the recommended Phase II pediatric veledimex dose (Section 7.5). Based upon this review, the SRC will make a recommendation that the cohort either continue at the existing dose, at a lower dose level, or other measures to be undertaken including discontinuation of treatment. If it has been determined that escalation or cohort expansion should not proceed, dose de-escalation may be undertaken and the SRC will consider de-escalating the veledimex dose as follows: 
 De-escalation by increments of 5 mg from the cohort in which 2 or more DLTs were observed (e.g., 15 mg down from 20 mg). If there are 2 or more DLTs in the dose de-escalation cohort, the SRC will consider de-escalating the veledimex dose by additional increments of 5 mg (e.g., 5 mg down from 10 mg) or declaring a previously studied dose level the recommended Phase II pediatric dose. 	2 to 6

After completion of a cohort, if it has been determined that the recommended Phase II pediatric dose has not been reached, escalation to the next cohort will proceed once recommended and authorized by the SRC.

